During the COVID-19-related suspension of in-person interactions with research participants, in-person group trainings and one-on-one trainings cannot take place. Those patients who have already been invited to attend an in-person training and expressed interest in attending will be invited to attend a virtual training instead through VA Video Connect (VVC) or a similar virtual modality such as Zoom. They will also be informed that an in-person training *may* be offered in the future. The virtual group and one-on-one trainings will follow the same format as the in-

person trainings. The VA trainer will share screens showing YouTube videos, Powerpoint slides, guidance documents and the My HealtheVet test account. The trainer will provide virtual guidance as the participants practice logging into and exploring their own My HealtheVet accounts.

Unless the administrative hold on in-person interactions with human research subjects lifted at the time when invitation letters are mailed to participants randomized to Encouragement Arm 3 for the one-on-one trainings, we will mail the amended letter inviting participants to an online training instead.

In this protocol, whenever “group trainings” or “in-person trainings” are mentioned, during the COVID-19-related suspension of in-person interactions with research participants starting 3/18/2020, these trainings refer to virtual trainings.

If the COVID-19-related suspension of in-person interactions with research participants is lifted before the study is completed, then in-person group trainings and one-on-one trainings may be offered again to the invited patients. If it no longer fits into the timeline of the study to offer the trainings, they will not be offered.

All Veterans will be invited to participate in the phone interview, regardless of which arm they are in, or whether they participated in in-person trainings that might have been offered to them. At the end of the Aim 3 intervention, all Comparison arm study participants who did not opt out or did not have an undeliverable mail address will be mailed a training guide.

5. Study Subject Selection

Sample Description

All participants will be Veterans aged 18 and older.

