This aim builds on prior study aims and involves the refinement and pilot testing of an intervention. Using a randomized encouragement design, we will randomize 200-300 Veterans ages 18-85 years old from the Bedford/Boston VAMCs with uncontrolled diabetes ($HbA1c > 8.5$) and no or minimal prior history of using the key MHV features to receive an invitation to one of the following groups, after they have been mailed a brochure and have had the opportunity to opt out of the study. We will aim for each encouragement arm to have at least 50 Veterans, and for the comparison arm to have 50+ enrolled Veterans.

- 1) Comparison arm: My HealtheVet brochure only
- 2) Encouragement arm 1: My HealtheVet brochure and training guide
- 3) Encouragement arm 2: My HealtheVet brochure and training guide plus offering a group training

- 4) Encouragement arm 3: My HealtheVet brochure and training guide plus offering a group training and a one-on-one session

We estimate that 15 to 25 (30-50 percent) of those randomized to each of the 3 encouragement arms will choose to participate by using the training guide or attending a group training or one-on-one session. Feedback on the intervention and patients' intent to use MHV will be gathered from the patient at the one-on-one meeting, the group session, and during their phone interview.

a. Subject Inclusion Criteria

Our primary inclusion criteria are that Veterans:

- Are current VA Bedford or VA Boston patients (including CBOC patients)
- Have uncontrolled diabetes ($HbA1C \geq 8.5$ at last test)
- Are inactive users (registered but with at least 1 year of non-use) or non-users of My HealtheVet
- Have an upcoming health visit scheduled at Bedford VA or Boston VA.
- Are age 18-85 years old at approximate time of first mailing

b. Subject Exclusion Criteria

Veterans are excluded if they do not meet the above criteria (e.g., they are already active MHV users, their most recent HbA1c at the time of recruitment was $< 8.5\%$, or they are age 86 and over at the time of the initial mailing).

c. Recruitment

Subject Identification and Pre-Enrollment Screening:

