Local Veterans from the Bedford/Boston VA healthcare systems ages 18-85 years old with uncontrolled glucose ($A1c > 8.5$) who have not used the patient portal or have only minimally used it in the past (and have had no use in at least the past 12 months), will be recruited for the study. Based on data from March 2019, we estimate this sample to be 170 eligible Veterans in Bedford and 539 eligible Veterans in Boston. We will mail the My HealtheVet brochure, welcome letter, information sheet, and an opt-out card with prepaid postage to all Bedford Veterans who meet eligibility criteria. All those that do not opt-out within 10 business days by telephoning or returning the opt-out card will be considered enrolled, and will be randomized to one of four arms:

- 1) Comparison arm: My HealtheVet brochure only
- 2) Encouragement arm 1: My HealtheVet brochure and training guide
- 3) Encouragement arm 2: My HealtheVet brochure and training guide plus offering a group training for how to use key My HealtheVet features

- 4) Encouragement arm 3: My HealtheVet brochure and training guide plus offering a group training and a one-on-one session

Based on the opt-out rate of Bedford patients, subsequent round(s) of mailings will be sent to Boston patients in order to have at least 50 patients enrolled in each encouragement arm and at least 50 patients enrolled in the comparison arm and a total of 200-300 total enrolled across both sites.

HIPAA Authorization for Recruitment and/or Screening:

A HIPAA waiver of authorization is required. It is necessary to obtain HIPAA identifiers (e.g., contact information and study eligibility) to contact participants for recruitment purposes.

Consent for Recruitment and/or Screening:

We have requested a waiver of consent for recruitment and/or screening. To help identify potential eligible participants (e.g., study eligibility, contact information), it will be necessary for us to obtain a waiver of consent for recruitment purposes.

Enrollment:

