Patients will be considered enrolled in this portion of the study if they do not opt out of the study. If participants opt out after randomization (by returning the opt-out postcard or leaving a voicemail message for the project staff), we will no longer contact them for other portions of the study. Not participating in an in-person training or a telephone interview will not be considered opting out. However, even if patients opt out, we will still look at data that we already have for these participants from previous study aims. Those receiving the information sheet (modified consent form) will be informed of the general nature of the study, what their involvement entails, the risk/benefits, and a description of confidentiality. Participants will be told that participation is voluntary, that they can withdraw at any time, and that this will not impact their treatment.

HIPAA Authorization:

This is a minimal risk study and we are requesting a waiver for the study.

We will protect identifiers, as outlined in this protocol (see **Data Security**) and destroy the identifiers in accordance with the VA records control schedule. PHI will not be used and or disclosed to any other person or entity, except as required by law, for authorized oversight of the

research study, or for other research for which the use of disclosure of the requested information would be permitted by the Privacy Rule.

Because study materials will be distributed via mail, we are requesting a HIPAA authorization waiver. Additionally, a HIPAA authorization waiver is necessary because requiring participants to complete and return a HIPAA waiver may bias our study results (i.e., those who return the waiver may have different clinical profiles or experiences on My HealthVet (i.e., be more active) than those who might not return the form).

We will protect identifiers, as outlined in this protocol (see modified consent form or information sheet) and destroy the identifiers in accordance with the VA records control schedule. PHI will not be used and or disclosed to any other person or entity, except as required by law, for authorized oversight of the research study, or for other research for which the use of disclosure of the requested information would be permitted by the Privacy Rule.

Informed Consent:

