Data analysis requires the use of information regarding enrolled patients' usage of My HealthVet for both recruitment and analysis, which would be biased if consent were required. We already have access to data describing their use of My HealthVet via a previous study Aim, therefore we are requesting a waiver of documentation of consent. We will provide all participants with an information sheet (modified consent form) containing information about their rights and any risks of participation, as well as study team contact information, with the initial mailing so that they will have time to review it prior to deciding whether or not to opt-out of the study.

6. Data Collection/ Study Measures

Data Collection:

For each in-person component of the intervention (group trainings and one-on-one sessions), Veterans will be asked to complete an immediate post-intervention feedback evaluation measuring their intent to use features of My HealthVet covered in the trainings. We will follow all Veterans randomized to the encouragement arms and comparison for 4-6 months and measure the number of My HealthVet features used, and the frequency with which they use them. We will look at My HealthVet use data of everyone invited to participate in the study.

Beyond this quantitative data, we will also conduct a semi-structured phone interview and demographic questions with Veterans in all arms at 4-6 months, seeking feedback on the intervention components and on their continued intent to use MHV for communication and

information sharing with VA and non-VA providers. The interview will be expected to last 15-20 minutes. We will not audiotape interviews. The interviewer will take notes on paper and/or enter responses into a secure VA REDCap database.

Feasibility data on the resources and time expended for intervention delivery will also be gathered to inform future implementation. All project staff will document hours spent planning training sessions, running training sessions, and interacting with participants over the phone. We will also document costs expended on printed materials and any other incurred project expenses.

7. Planned Statistical Analyses

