their use patterns in 2014 to estimate behavior in the control. Among diabetics who did not use MHV in 2013, 98% were still not using in 2014, 1% were using at least one feature, and 1% were using more than one feature. A priori estimates are that 30% of Veterans will comply with the encouragement they are randomized to, and among those, 50% will use MHV at least once. With these assumptions, we have 80% power (alpha 0.05) to detect a difference in Intent-to-Treat analysis with a sample of 70 per arm. Although we do not know the exact number who will comply or will go on to use the system, we feel that it is reasonable that half of those who receive the encouragement will begin to use.

8. Ethical Issues

a. Risks

The risks of the study are minimal in that the probability and magnitude of harm or discomfort anticipated in the research are not greater in and of themselves than those ordinarily encountered in daily life or during the performance of routine physical or psychological examinations or tests. Participants will be asked about their diabetes management and how they use My HealthVet.

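### Enrolment by silence has no check for returned mail, so Veterans whose packet never arrived can be randomized uninformed and dilute the ITT contrast

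*Combined protocol and SAP*

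**What the plan says.** Enrolment rests on the absence of an opt-out. Section 5c (Subject Identification and Pre-Enrollment Screening) says "All those that do not opt-out within 10 business days by telephoning or returning the opt-out card will be considered enrolled", with randomization to four arms next. The Enrollment paragraph of the same section repeats it: "Patients will be considered enrolled in this portion of the study if they do not opt out of the study". Section 4 has the same rule, with a window of approximately 10 business days.

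Section 5b adds no condition about delivery: "Veterans are excluded if they do not meet the above criteria", and those criteria do not mention mail. Nowhere does the protocol describe taking returned packets out before allocation.

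Two statements assume that the packet arrives. The Sample Description in Section 5 places randomization after the brochure mailing and an opportunity to opt out. The Informed Consent paragraph in Section 5c says "We will provide all participants with an information sheet (modified consent form) containing information about their rights and any risks of participation", sent with the initial mailing so that it can be read before deciding.

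One statement expects that some mail does not arrive. At the end of Section 4, "all Comparison arm study participants who did not opt out or did not have an undeliverable mail address will be mailed a training guide".

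**The concern.** A Veteran whose packet is returned cannot send back an opt-out card that never came. Read literally, the rule turns that silence into enrolment. The clause on the end-of-study guide mailing suggests that the authors expect undeliverable addresses among comparison participants who have already been randomized.

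Two things are at stake. First, documentation of consent is waived, and the initial mailing is the only notice described before enrolment. A Veteran who did not get it is in the trial without the information sheet or the chance to decline. This needs no assumed rate.

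Second, these Veterans fill places. Later mailing rounds are sized on the opt-out rate alone, so undelivered packets count toward the 50 per arm. The ITT analysis keeps everyone by randomized arm. Those whom the encouragement cannot reach pull the contrast toward zero and lower the engagement rate on which the complier average causal effect (CACE) analysis depends.

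**Working it through.** **Inputs from Section 7 (Power).**
- Comparison-arm use: "98% were still not using in 2014, 1% were using at least one feature, and 1% were using more than one feature", so any use is 1% + 1% = 2%.
- Compliance: "A priori estimates are that 30% of Veterans will comply with the encouragement they are randomized to".
- Use among compliers: 50%. Encouragement-arm use is therefore 0.30 × 0.50 = 15%.
- Alpha 0.05 (two-sided assumed; not stated), 80% power, 70 per arm. Section 7 names the chi-square test for the ITT analysis.

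**Plan's own figure.** For 2% versus 15%, one encouragement arm against comparison, the pooled-variance normal approximation needs 72 per arm and gives 79.4% power at 70. The stated 70 per arm reproduces. Exact enumeration of the uncorrected Pearson chi-square test gives 85.3% at 70 per arm and 68.9% at the recruitment minimum of 50. The exact figures are used below; the approximation shows the same pattern.

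**Assumed input.** The protocol gives no undeliverable share u. I take u = 5, 10 and 20%, and let undeliverable Veterans use the portal at the comparison rate of 2%.

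**Reading A: the 30% applies only to reachable Veterans.** Encouragement-arm use is (1 − u) × 15% + u × 2%. For u = 10%: 0.90 × 15% + 0.10 × 2% = 13.7%, so the difference from comparison shrinks from 13.0 to 11.7 points.

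| u | Use in encouragement arm | Power, 70 per arm | Power, 50 per arm |
|---|---|---|---|
| 0 | 15.0% | 85% | 69% |
| 5% | 14.35% | 82% | 65% |
| 10% | 13.7% | 79% | 62% |
| 20% | 12.4% | 72% | 54% |

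**Reading B: the 30% is of everyone randomized.** Undeliverable Veterans are already among the 70% who do not comply, so planned use stays at 15% and planned power is unchanged. If only deliverable Veterans were randomized, their rate p would solve (1 − u) × p + u × 2% = 15%, so p = 2% + 13%/(1 − u).

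| u | Use, deliverable only | Power, 70 per arm | Power, 50 per arm |
|---|---|---|---|
| 0 | 15.0% | 85% | 69% |
| 5% | 15.7% | 88% | 72% |
| 10% | 16.4% | 90% | 76% |
| 20% | 18.25% | 94% | 83% |

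**By arm.** In arm 1 the guide is mailed and nothing else is offered, so the 2% assumption fits. For group and one-on-one training, Section 4 also has staff telephone the Veteran, so some with a bad address may still engage. For arms 2 and 3 the tables therefore give an upper bound on the dilution.

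**Replacement.** Section 4 counts 170 + 539 = 709 eligible Veterans for 200 to 300 places.

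**The case against.** The strongest reply is that the power loss may be counted twice. The compliance figure is worded over Veterans as randomized, and the Sample Description does the same: "We estimate that 15 to 25 (30-50 percent) of those randomized to each of the 3 encouragement arms will choose to participate". Non-receipt is one way of not complying. On that wording, the natural one, the plan's power stands. A reader might infer from Reading A that the trial falls short of its stated 80%; the documents do not show that. Even on Reading A, exact power at 70 per arm is 82% at u = 5% and 79% at u = 10%; only the assumed 20% costs much. The 69% starting point at 50 per arm comes from the gap between the recruitment minimum and the 70 in the power statement, which is a separate matter.

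A reader might also infer that the protocol knowingly randomizes Veterans whose packet came back. It does not say so. The clause about undeliverable addresses is loosely worded and does not say when they were found. An address could fail during the 4 to 6 months of follow-up, or a packet could come back after the opt-out window. The Sample Description, with its opportunity to opt out, could even be read as keeping such Veterans out. What stands against this is that no operative step does so, and three statements of the enrolment rule omit it.

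To say that these Veterans cannot be encouraged at all would be too strong for arms 2 and 3, given the telephone calls. Nor is there bias: non-receipt that is equal across arms leaves a valid estimate of offering encouragement to those enrolled. Additional never-takers cost the CACE analysis precision without changing the complier effect. Failure to reach people by mail is also a feasibility result in itself. All of this stands. It limits the size of the problem but does not supply the missing rule.

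**Conclusion.** The point holds as a gap in the enrolment rule. As written, Veterans whose initial packet was returned can be enrolled and randomized, contrary to the protocol's own statements about the information sheet and the opportunity to opt out. That part needs no assumption beyond the text.

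The statistical cost is dilution of unknown size. For u between 5 and 20%, it is a loss of about 3 to 14 percentage points of power at 70 per arm if the 30% applies to reachable Veterans only (85.3% to 82.5% and 71.7%). It is a forgone gain of about 3 to 9 points if the 30% covers all randomized (85.3% to 87.8% and 94.4%). On both readings, a deliverable-only sample of the same size has more power. The figures rest on an assumed u, 2% use among undeliverable Veterans, a two-sided test, and one arm against comparison. A shortfall against the planned 80% is not established.

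**What to change.** In Sections 4 and 5c, add to the enrolment rule that a Veteran whose initial packet is returned undeliverable before randomization is not enrolled or randomized, and is replaced from the eligible pool. In addition:

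- Randomize each mailing round only after returned mail has been checked, and state how long that wait is.
- Size later rounds on opt-outs plus returned mail, not on opt-outs alone.
- Keep anyone found unreachable after randomization in the ITT set.
- Report the undeliverable count before randomization, and by arm afterwards.
- State in Section 7 whether the 30% compliance includes Veterans who do not receive the mailing.

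The exclusion precedes allocation, so it cannot bias the comparison between arms. The cost is a few sentences, a short wait per round, and results that apply to Veterans reachable by mail. That last limit suits an intervention delivered or initiated by mail, but should be stated.

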Participants will be recruited from two VA medical centers, Bedford and Boston VA. Analyses will be conducted at Bedford ENRM VA Hospital.

Study Related Procedures

We will conduct a small-scale experiment using the sites of the CHOIR center (Bedford/Boston). Participants will be identified who:

- Are current VA Bedford or VA Boston patients (including CBOC patients)
- Have uncontrolled diabetes ($HbA1C \geq 8.5$)
- Are inactive users (registered but with at least 1 year of non-use) or non-users of My HealthVet
- Have an upcoming health visit scheduled at Bedford VA or Boston VA.
- Are age 18-85 years old at approximate time of first mailing

CPRS/VistA chart review and administrative data extraction (VSSC files and CDW tables) will be used to identify potential participants and to identify mailing addresses for the patients to be invited to participate Aim 3. As of March 2019, there were 170 eligible patients in Bedford and 539 eligible patients in Boston. (We expect these numbers to shift slightly as new appointments are made or diabetes control changes among the populations.).

All Veterans selected to participate based on these criteria will be sent a mailing including a brochure with information on My HealthVet, a welcome letter introducing the study, an information sheet (modified consent form), and an opt-out card.

All eligible Bedford patients will be invited to participate in a first round of mailings. Based on the opt-out rate of Bedford patients, subsequent round(s) of mailings will be sent to Boston patients in order to have at least 50 patients enrolled in each encouragement arm and at least 50 patients enrolled in the comparison arm (see information about arms in following paragraphs; 200-300 maximum overall across sites).

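### Portal non-use is screened before a promotional mailing and not re-checked at randomisation, so any Veteran who starts in the gap is randomised; the cost is power, possibly very little.

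*Combined protocol and SAP*

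**What the plan says.** **Eligibility.** Section 5a admits Veterans who "Are inactive users (registered but with at least 1 year of non-use) or non-users of My HealtheVet", and section 5c adds "and have had no use in at least the past 12 months". Section 5b excludes Veterans if "they are already active MHV users", without saying on what date that is judged. Among the inclusion criteria, only age is dated to the mailing: "Are age 18-85 years old at approximate time of first mailing".

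**Mailing.** Under section 5c the package goes "to all Bedford Veterans who meet eligibility criteria", so eligibility is applied before it is sent. Section 4 says that all those selected "will be sent a mailing including a brochure with information on" the portal. The brochure is also the whole of the comparison condition.

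**Randomisation.** Section 5 (Sample Description) places it "after they have been mailed a brochure and have had the opportunity to opt out of the study". The opt-out window is about 10 business days (section 4; section 5c omits the qualifier). Section 5c then states that those who do not opt out "by telephoning or returning the opt-out card will be considered enrolled, and will be randomized to one of four arms".

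**Outcome.** Section 6 follows everyone randomised for 4-6 months but does not say when that period starts. It also says that portal-use data will be examined for everyone invited. Section 7 makes the primary analysis intent-to-treat by randomised arm.

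**The concern.** The trial asks whether encouragement turns non-users into users. Non-use is established, a document promoting the portal is sent, and only then are Veterans randomised. Nobody looks again at whether they are still non-users, and no rule covers use in the gap. Because the start of follow-up is not stated, such use could even be counted as outcome.

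A Veteran who has already started adds little or no contrast on any use, the outcome the trial is powered on. That person tends to be a user in every arm. The planned comparison rate is 2%, about one user in an arm of 50 (50 × 0.02 = 1), so one extra user per arm is a large relative change in the background on which the power rests.

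That non-use is fixed before the mailing is an inference from the order of steps. The plan does not state it.

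**Working it through.** **Inputs (section 7, Power).** Comparison rate 1% + 1% = 2%. Encouragement rate 30% × 50% = 15%. Alpha 0.05, taken as two-sided because the plan does not say. Stated result: 80% power with 70 per arm. Section 4 sets a floor of 50 per arm.

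**1. Reproduce the plan's figure.** With pooled variance, no continuity correction, and mean rate (0.02 + 0.15)/2 = 0.085:

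n = [1.96√(2 × 0.085 × 0.915) + 0.8416√(0.02 × 0.98 + 0.15 × 0.85)]² / 0.13² = (0.773 + 0.323)² / 0.0169, which rounds up to 72 per arm.

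Power at 70 per arm is 79.4%, so the plan's figure reproduces. At 50 per arm it is 64.9%.

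**2. The documents' only anchor for early starting.** Among pilot non-users, 2% were using the portal in the following year. Taking 10 business days as 14 calendar days: 0.02 × 14/365 = 0.00077, about 0.08%. In 300 Veterans that is 0.23 of a person.

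**3. Power when a share e has started before randomisation.** The documents give no value for e after a brochure, so it is an assumption shown over a range. Every early starter is assumed to count as a user in follow-up.

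- Model A, starting unrelated to response to encouragement: comparison = e + (1 − e) × 0.02; encouraged = e + (1 − e) × 0.15.
- Model B, worst case, where every early starter would have used the portal under encouragement anyway: comparison = 0.02 + e; encouraged = 0.15.

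| e | A: rates | A: difference | A: power, 70 per arm | A: power, 50 per arm | B: power, 70 per arm |
|---|---|---|---|---|---|
| 0 | 2.0% v 15.0% | 13.0 points | 79.4% | 64.9% | 79.4% |
| 0.08% | 2.08% v 15.07% | 13.0 points | 79.0% | 64.4% | 78.7% |
| 1% | 2.98% v 15.85% | 12.9 points | 74.7% | 59.9% | 70.3% |
| 2% | 3.96% v 16.70% | 12.7 points | 70.1% | 55.4% | 60.4% |
| 5% | 6.90% v 19.25% | 12.4 points | 58.3% | 44.8% | 32.6% |

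Under Model A the difference hardly moves; the loss comes from the larger variance at higher rates. Under Model B the difference itself shrinks, to 11.0 points at e = 2% and 8.0 points at e = 5%.

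**4. Sensitivity to the encouragement rate.** If the 70% who do not comply also start at 2%, that rate is 0.15 + 0.70 × 0.02 = 16.4%. Model A power at 70 per arm is then 84.6%, 84.3%, 80.6%, 76.6% and 65.5% at the same five values of e. The pattern is unchanged.

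**5. With a re-check.** Removing early starters restores 2% versus 15% in a slightly smaller sample. At e = 1% or 2%, 70 per arm becomes 69 and power is 78.8%. At e = 5% it becomes 66 and power is 77.0%. With replacement it returns to 79.4%. These figures assume no further brochure-prompted starts after randomisation.

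**The case against.** The strongest objection is size. Nothing in the documents shows that 1-5% start within two weeks, and the one rate they give implies almost nobody. Section 2 adds a practical barrier: secure messaging, lab views and record extracts need an account authenticated in person, which a true non-user is unlikely to complete in about 10 business days. This stands as a reason to think e is small. It does not show that e is zero. Prescription refill needs only registration, some inactive users may already be authenticated, and the documents mention no brochure mailing to the pilot non-users behind the 2%.

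A reader might infer that the comparison is biased. It is not. The brochure precedes randomisation and is common to all four arms, so early starters are balanced in expectation and the contrast remains the effect of encouragement on top of the brochure.

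A reader might also infer that an early starter cannot respond to the guide or training. That is arguable only for any use. The hypothesis in section 3 concerns the number and variety of features, and sections 6 and 7 also measure frequency; someone who has tried one feature can still be moved on all of these.

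Finally, a re-check removes only those who start before randomisation. Later brochure-prompted starts remain in every arm and can still lift the comparison rate above 2%.

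**Conclusion.** The gap is real. The enrolment rule in section 5c can randomise a Veteran whom section 5b excludes as an active user, and the handling of use between mailing and randomisation is undefined. The consequence is lost power on any use, not bias.

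Its size is unknown. At the background rate it is 0.4 of a point at 70 per arm under Model A and 0.7 under Model B. It becomes material only if the brochure prompts about 1-2% to start within the window: 79% then falls to 75-70% under Model A, or to 70-60% in the worst case. These figures assume a two-sided pooled test of one arm against comparison and that every early starter counts as a user.

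The documents do not support saying that Veterans have in fact started before randomisation, or that the effect is substantially diluted: under Model A at e = 2% the difference falls only from 13.0 to 12.7 points. The point is worth acting on because the remedy is nearly free and costs little power even if e is negligible.

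**What to change.** **Enrolment rule (section 5c).** Change it so that those randomised are the Veterans who do not opt out and who have no logged My HealtheVet feature use between the eligibility pull and the day of randomisation. Re-pull usage once per batch, just before randomising.

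**Outcome window (section 6).** State that the 4-6 months, and the count of outcome use, start at randomisation.

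**Batches already randomised.** Keep the all-randomised intent-to-treat analysis as primary, since section 7 defines it by randomised arm. Add a sensitivity analysis that excludes, in all four arms, Veterans with logged use before their randomisation date. Because that use precedes randomisation, excluding on it preserves the randomised comparison. Making it primary after the fact would replace the plan's own analysis.

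**Cost.** One extra pull per batch of data that the study already uses for recruitment and analysis (section 5c, Informed Consent). A few Veterans may need replacing, for which the 539 eligible in Boston as of March 2019 give room. The result will apply to Veterans whom the brochure alone had not already moved by the time of randomisation, and the report should say so.
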